10.2.2 Participant Recruitment

Eligible participants for this study will be recruited from among children present in the hospital's Healthy Children and Vaccination Service, known informally as the immunization clinic (*Centro de Vacunas*).

The HIRRC immunization clinic is located in a satellite building on the ground level just steps from the main outpatient building, and draws a heterogeneous patient population because it is known for having a consistent supply of vaccines. Many parents bring children long distances to receive immunization services in this popular facility. A review of those receiving measles vaccine at the immunization clinic (when the recommended age was 9 months) in the full six months from February through July 2003, identified a total of 718 patients of age \geq 9 -to- <12 months in which both date of birth and age of vaccination were recorded in the medical record (personal communication, [name], 2003). This represents an average of 120 patients per month, or 28 per week, in an age range that is only one-sixth of the target age range for recruitment into this study of \geq 6 -to- <24 months.

Parents of potential participants in the waiting room of the *Centro de Vacunas* will be solicited for interest in the study and invited to learn more at the *Centro del Estudio* [Study Center]. See section 10.6.2.

10.2.3 Study Center

A suite of two rooms (office and injection room) is renovated on the 2^{nd} floor of the main outpatient building for use as the planned research study center (*Centro del Estudio*) for this trial. Chairs in a waiting area are located immediately outside the suite. The physician investigator's office where medical history and clinical examinations will be performed is located about 15 meters down the hall. In these rooms, the orientation, interview, and explanation of the informed consent will be conducted with the parents, and the child either recruited at that time, dismissed as ineligible, or scheduled to return at a later date upon reaching eligibility. Vaccinations and return followup visits will occur in the Study Center.

10.3.2 Exclusion Criteria

To be excluded are infants WHOSE PARENT(S)/LEGAL GUARDIAN(S) ... :

- a. are unable or unwilling to give written informed consent for their infant to participate in the study
- b. cannot be contacted by telephone (family's own or a neighbor's) by the study nurse if necessary for surveillance of adverse events if scheduled followup return appointments are not fulfilled
- c. are unable to complete the diary form for adverse events, to measure and record temperature with the TraxIt[™] skin-appliqué thermometer, to measure the maximal diameter of local reactions or limb circumference, or have difficulty reading or understanding written instructions, or other factors which indicate exclusion in the judgment of the study staff

Also to be excluded are INFANTS who ... :

- d. have fever (by parental report or by rectal temperature ≥38.5° C or axillary ≥38.0°
 C) currently or within the past 3 days, or who are currently suffering from an acute or chronic infectious disease (including known HIV)
- e. have had an acute or chronic infection requiring systemic antimicrobial therapy (antibiotic or antiviral) or other prescribed treatment within the past 21 days. This includes any underlying illness that may limit their response to vaccination, such as those receiving intravenous immunoglobulin for agammaglobulinemia, or systemic steroid therapy
- f. are malnourished, defined by weight less than two standard deviations below the median weight for their age
- g. are allergic to eggs, or have a history of any anaphylactic shock, asthma, urticaria, or other allergic reaction after previous vaccinations, or have allergy or hypersensitivity to any component of the study vaccine
- h. have ever received previously any influenza vaccine
- i. have received within the prior 28 days, or for whom there is the indication to receive in the next 56 days, any non-study vaccination or investigational agent outside of the study (This would exclude infants "behind schedule" and needing to receive on the day of first interview protection against tuberculosis, polio, diphtheria, tetanus, pertussis, hepatitis B, *Haemophilus influenzae* type b, measles, mumps, or rubella. See section 10.4.7 for the effect on recruited age ranges)
- j. have a known bleeding diathesis, or any condition that may be associated with a prolonged bleeding time
- k. have currently any serious confirmed or suspected disease, such as metabolic, cardiac, or autoimmune disease, or diabetes
- 1. have a history of epilepsy or a seizure disorder, or neurodevelopmental disorders such as autism
- m. have a genetic anomaly or known cytogenic disorder (e.g., Down's syndrome)
- n. have leukemia, lymphoma, or any other cancer/neoplasm
- o. have known or suspected immune dysfunction, including HIV infection, or receives now or in the past immunosuppressive therapy, including the use of steroids associated with the suppression of the hypothalamic-pituitary-adrenal (HPA) axis (systemic corticosteroids, e.g., 1 mg/Kg/day of prednisone or its equivalent, or the chronic use of inhaled high-potency corticosteroids, e.g., 800 μg per day of budesonida or 750 μg per day of fluticasone)
- p. have ever received blood, blood products, or parenteral preparations of immunoglobulin
- q. have any other serious disease (e.g., with signs of cardiac or renal failure), including progressive neurologic disease
- r. have any condition which, in the opinion of the investigator, may interfere in the evaluation of the objectives of the study

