10.4.5 Timing of Doses for Each Participant

Upon obtaining informed consent from participants, all participants will receive a dose of influenza vaccine at day 0 (zero) by one of the three dosages and routes of administration (see section 10.1.1). After followup return visits in person to assess adverse reactions scheduled on days 2 and 7, each participant will return for a second dose of vaccine on day 28 (4 weeks), which will be followed again with return visits for adverse reactions on days 30 and 35. A final visit on day 56 (8 weeks) will be scheduled for the third and final blood draw and an "insurance" dose of full-strength vaccine administered by conventional needle-syringe. The days listed above for followup visits and actions have various margins of acceptable deviation, as listed in **Table 6** in section 10.6.1.

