10.4.7 Prior and Concomitant Therapy - Other Vaccinations

No other routine or investigational vaccines will be administered within 28 days before or after either of the study's investigational **INF** doses 1 or 2. As per the study exclusion criteria (see paragraph i. in section 10.3.2), otherwise eligible participants will not be recruited if they have received in the prior 28 days any routinely recommended vaccinations of the current Dominican Republic public immunization policy, or are due

HIRRC/CDC Needle-free Intradermal	Page 76	File: 4785-ID-INF-Prot-Engl-2008Jun24.doc
Influenza Study - CDC-ISO-4785	of 138	2008-Jun-24

to receive them in the following 56 days. The recommended Dominican immunization schedule indicates vaccines at 6 months (**POL**_{OPV}, **DTP**_w-**HBV**-**HIB**), 12 months (**MMR**), and 18 months (**POL**_{OPV}, **DTP**_w-**HBV**-**HIB**) of age. ^{SESPAS}

This restriction thus excludes infants "behind schedule" and needing to receive on the day of first interview protection against tuberculosis, polio, diphtheria, tetanus, pertussis, hepatitis B, *Haemophilus influenzae* type b, measles, mumps, or rubella. It also creates three gaps in the intended ≥ 6 -to- <24 months age range of recruited participants for this study. The first gap would be ages <7 months (unless the participant received his or her third **POL**_{OPV} and **DTP**_w-**HBV**-**HIB** doses at ≤ 5 months); the second gap from >10 -to- <13 months; and the third gap from >16 -to- <19 months.

If, in the opinion of the Dominican investigators, a child may benefit by immediately receiving another vaccine during the 28-day-period after either of the study's influenza vaccine doses (e.g., because of exposure to meningitis or another vaccine-preventable disease), such other vaccines should be administered by the appropriate authority and duly noted on the Case Report Form, part 20.

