10.6 Study Procedures

10.6.1 Time and Events Table

The sequence and chronology for conducting clinical and diagnostic activities is summarized in **Table 5**. Allowable variations from the planned schedule of followup visits are detailed in **Table 6**.

Table 5. Time and events				d	ays*			
Procedure / Test	0	2	7	28	30	35	56	56d + 6 months
SCREENING – recruitment, informed consent, medical history	√							
EXAM – weight, height, limb circumference, temperature, local/systemic reactions	~	✓	~	~	~	~	~	
BLOOD SAMPLE for hemagglutination inhibition serologies	~			~			~	
VACCINATION with INF vaccine by blinded dose and route	~			~				
PHOTOGRAPH of INF injection site, closeup with scale	*	~	~	*	✓	~		
REVIEW and discuss parent diaries; collect completed ones		~	~	~	✓	~	~	
"Insurance" VACCINATION 0.25 mL INF IM by N-S ⁺							✓	
"Bonus" booster VACCINATION 0.25 mL INF IM by N-S; inquiry on intervening adverse events								\checkmark

* See next table for acceptable windows for scheduled visit and followup dates.

† Groups IM-NS-0.1 and ID-JI-0.1 receive full dose. Group IM-NS-0.25 receives mock injection.

‡ Photography only if any injury or persistent local reaction is visible to be photographed.

Table 6. Acceptable windows for followup visits

Intended day	Day to be	Permitted	Earliest		Latest
since 1 st	scheduled	variation	permitted	Latest permitted day	weeks

HIRRC/CDC Needle-free Intradermal	Page 84	File: 4785-ID-INF-Prot-Engl-2008Jun24.doc
Influenza Study - CDC-ISO-4785	of 138	2008-Jun-24

	vaccination	since last	from	day since			since 1 st
Visit		vaccination	scheduled	1 st vacc.	since	since	vacc.
no.			day		1 st vacc.	2^{nd} vacc.	
1	"Day 0"	0					
2	"Day 2"	+2	+/- 1 day	1	3		0.4
3	"Day 7"	+7	+/- 1 day	6	8		1.1
4	"Day 28"	+28	+ 14 days	28	42		6.0
5	"Day 30"	real 2 nd -	+/- 1 day	29	45 *	3	6.4 *
		dose day					
		+2					
6	"Day 35"	real 2 nd -	+/- 1 day	34	50 *	8	7.1 *
		dose day					
		+7					
7	"Day 56"	real 2 nd -	+ 28 days	56	98 *	56	14 *
		dose day					
		+28					
8	8 months	+6 months	+3 months	8 months	98 +	56 +	53 *
					9 months	9 months	

* Assumes 2nd vaccination at latest permissible day (42) since 1st vaccination.

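### The 56-day look-ahead for due vaccines fits only a dose 2 on day 28; with dose 2 permitted to day 42, screening does not secure the 28-day separation on days 57 to 70

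*Protocol*

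**What the plan says.** - **Screening rule.** Protocol 10.3.2, exclusion i, excludes infants "for whom there is the indication to receive in the next 56 days" a non-study vaccine. Section 10.4.7 restates it for routine vaccines that a child is due "to receive them in the following 56 days".
- **Separation rule.** Section 10.4.7: "No other routine or investigational vaccines will be administered within 28 days before or after either of the study's investigational" influenza doses 1 or 2. The Synopsis (Concomitant vaccines) says the same and presents recruitment timing as the way to achieve it: children are not to be enrolled at unsuitable intervals around their routine doses.
- **Age gaps.** Section 10.4.7 derives gaps in the recruited ages from the rule, including "the second gap from >10 -to- <13 months; and the third gap from >16 -to- <19 months", ahead of the vaccines scheduled at 12 and 18 months.
- **Dose 2 timing.** Section 10.4.5 puts dose 2 on day 28 and says that the listed days "have various margins of acceptable deviation, as listed in" Table 6. Table 6 (10.6.1) allows the day-28 visit 14 days late and never early. Its footnote reads "Assumes 2nd vaccination at latest permissible day (42) since 1st vaccination".
- **Exception.** The only exception in 10.4.7 is another vaccine judged to be of immediate benefit, for example after an exposure. It does not cover a scheduled dose that simply falls due.

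**The concern.** The look-ahead appears to be built from the nominal schedule, while the visit table gives dose 2 a two-week allowance in one direction only. Day 56 is therefore the earliest possible end of the 28 days after dose 2. A child who passes exclusion i, attends within the permitted windows and deviates from nothing can have a 12- or 18-month vaccine fall due while the 28-day bar is still running.

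No section tells staff what to do then. Either the routine vaccine is held back without a written instruction, or it is given inside the 28-day adverse event follow-up after dose 2. At 18 months the scheduled products listed in 10.4.7 include a whole-cell pertussis combination. What is at stake is some noise in the late unprompted event reports and an eligibility figure that the plan's own windows defeat.

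**Working it through.** **Inputs**
- Look-ahead: 56 days (10.3.2 i; 10.4.7), counted from day 0, since Table 5 places screening and dose 1 on the same day.
- Separation: 28 days (10.4.7).
- Dose 2: day 28 nominal, day 42 at the latest (10.4.5; Table 6).
- Age gaps: start just after 10 and 16 months; vaccines due at 12 and 18 months (10.4.7).

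**Step 1: the plan's own figure.** Required look-ahead = day of dose 2 + 28. With dose 2 on day 28: 28 + 28 = 56. The stated 56 days is reproduced exactly.

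**Step 2: the permitted window.**

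| Dose 2 on day | Protected period ends | Beyond the 56-day look-ahead |
|---|---|---|
| 28 | 56 | 0 days |
| 35 | 63 | 7 days |
| 42 | 70 | 14 days |

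The latest dose 2 that 56 days can cover is 56 − 28 = day 28, which is also the earliest permitted day.

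**Step 3: what the age gaps add.** From 10 to 12 months, or from 16 to 18 months, is 59 to 62 days, depending on the calendar months. A child enrolled at exactly 10 or 16 months is still eligible.
- Dose 2 on day 42: 70 − 62 = 8 to 70 − 59 = 11 days uncovered per due age.
- Dose 2 on day 35: 63 − 62 = 1 to 63 − 59 = 4 days uncovered.
- The gaps fully absorb a dose 2 up to day 59 − 28 = 31 to 62 − 28 = 34.

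Example: for a child of exactly 10 months with dose 2 on day 42, the 12-month vaccine is due 59 − 42 = 17 to 62 − 42 = 20 days after dose 2, inside the bar.

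**Step 4: share of eligible ages.** With the gaps applied, the eligible bands are 7–10, 13–16 and 19–24 months: 3 + 3 + 5 = 11 months, about 335 days. Two due ages are affected.
- Every dose 2 on day 42: 2 × 8 / 335 = 4.8% to 2 × 11 / 335 = 6.6%.
- Every dose 2 on day 35: 2 × 1 / 335 = 0.6% to 2 × 4 / 335 = 2.4%.

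The exposed children are those enrolled in the last days before reaching 10 or 16 months.

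**Step 5: where an intruding vaccine would land.** A vaccine that passes the 56-day screen is due on day 57 at the earliest. With dose 2 no later than day 42, that is at least 57 − 42 = 15 days after dose 2, and the bar ends at 28 days. Section 10.1.3.2 collects prompted local and systemic reactions for days 0–2 and 3–7, and only unprompted events for days 8–28.

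**The case against.** The best defence is that exclusion i is a screening rule and the 28-day separation is a rule of conduct. The separation runs from the actual date of dose 2 and bars giving another vaccine, not its falling due. All the rules could be met together by giving the routine vaccine after the window, a wait of at most 14 days, and 10.6.3 has the immunization clinic's own nurses serve as study nurses. This stands in part: a vaccine falling due is not itself a breach of 10.4.7. But the Synopsis makes recruitment timing the means of separation, and no section says that a scheduled dose is to be held back. Nor is a day-42 dose 2 a deviation; Table 6 permits it.

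Three stronger readings are tempting and not supported:
- A reader might divide the full 14 days by the 335-day span and get 2 × 14 / 335 = 8.4%. That takes the numerator from the 56-day rule and the denominator from the age gaps. With the gaps applied to both, the day-42 figure is 5 to 7%.
- A reader might count vaccines up to the latest final blood draw, day 98 in Table 6. The 28-day bar attaches only to doses 1 and 2, so no stated rule applies after day 70.
- A reader might infer that the prompted fever and local reaction comparison is contaminated. Step 5 shows that the uncovered days fall at least 15 days after dose 2, outside that window.

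**Conclusion.** The point holds as a minor internal mismatch. The 56-day look-ahead secures the stated separation only for a dose 2 on day 28, and the permitted window can carry the protected period to day 70. After the age gaps, 8 to 11 days per due age remain uncovered at the latest dose 2: about 5 to 7% of eligible ages if every child had dose 2 on day 42, and about 1 to 2% at day 35.

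These shares assume uniform enrolment ages over the 335 days and a common dose 2 day. They are illustrations, because the protocol gives no expected distribution of dose 2 dates; dose 2 is scheduled for day 28, so the day-42 figure is an upper case. Enrolment of some six-month-olds under the exception in 10.4.7 would lower them slightly.

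The consequence is an uninstructed deferral or some background in unprompted day 8–28 reports. With randomized blocks (10.4.4.1) and blinded observers (10.4.6), this should be similar across arms, and there is no reason to expect bias in the comparison.

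**What to change.** Reconcile three places so that they describe the same period: the 56-day look-ahead in 10.3.2 i, the 56 days and age gaps in 10.4.7, and the latest dose 2 day in Table 6 taken together with the 28-day separation. Which interval should change is a clinical and operational decision for the sponsor and investigators; this review does not propose one.

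The cost is one number in the exclusion criterion (with its restatement in 10.4.7) or in the visit table, plus the age gaps that follow from it. The downside is a slightly narrower set of eligible ages or a slightly narrower visit window.

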10.3.3 Removal of Participants from Therapy or Assessment

The parent(s) or legal guardian(s) of infant participants may withdraw consent for his/her/their child to participate in the study at any time without prejudice. At any time, the investigator may withdraw a participant if, in his or her clinical judgment, it is in the best interest of the participant or if the participant or parent(s) cannot comply with the protocol. Whenever possible, the tests and evaluations listed for the final visit should be carried out. The Dominican and U.S. Senior Investigators should be notified in a timely manner to discuss all study withdrawals.

10.4 Treatments

10.4.1 Treatments Administered

All recruited participants will receive the same influenza vaccine (INF), but in different antigen volumes, tissue compartments, or means of injection.

- Group "**IM-NS-0.25**" (controls) two full 0.25 mL vaccine doses administered one month apart intramuscularly (IM) by sterile needle of 22-25 gauge, with a minimum length of 25mm (1-inch), attached to a sterile disposable needle.
- Group "**ID-JI-0.1**" (investigational) two reduced 0.1 mL vaccine doses administered one month apart intradermally (ID) by sterile, disposable needle-free Biojector[®] Syringe [cartridge] #2 and Biojector[®] 2000 jet injector, fitted with an investigational spacer on the cartridge nozzle creating a gap of 2 cm between nozzle orifice and skin.
- Group "IM-NS-0.1" (investigational) two reduced 0.1 mL vaccine doses administered one month apart intramuscularly (IM) by sterile needle of 22-25 gauge, with a minimum length of 25mm (1-inch), attached to a sterile disposable needle intramuscularly (IM) by needle-syringe (NS)

One month after the 2nd dose of INF vaccine described above, participants in the two investigational groups (**ID-JI-0.1** and **IM-NS-0.1**) that received reduced doses will receive a 3rd "insurance" dose of 0.25 mL of the same vaccine intramuscularly (IM) by sterile needle-syringe. Controls (**IM-NS-0.25**) who already received the standard two full doses will receive a mock injection to avoid extravaccination. Six months later, all groups three groups will return for a "bonus" booster dose.

10.4.2 Identity of Investigational Vaccine

Figure 4. Vaxigrip® vaccine 5 mL vial (bilingual English-French label)

(Vaxigrip[®], Sanofi-Pasteur)

The Vaxigrip[®] brand of Inactivated Influenza Vaccine Trivalent Types A and B (Split Virion) to be used in this study (see Figure 4) is manufactured in Val De Reuil, France, by Sanofi-Pasteur (headquartered in Lyon, France and initially known as Institut Mérieux, then as Pasteur Mérieux Sérums et Vaccins, Pasteur-Mérieux-Connaught, and later Aventis Pasteur). The Vaxigrip[®] brand of influenza vaccine was first marketed in France in 1968. ^{Saliou2005} Current formulations were developed in the 1980s and first marketed in 1995. It uses octoxynol-9 (Triton[®] X-100) detergent to "split" the virus particles and render them less reactogenic, a technique that previously required an ether compound that was dangerous to handle in manufacturing. ^{Lina2000}

Vaxigrip[®] is currently licensed for sale and routine use of its prefilled syringe packaging format by the Dominican Republic national pharmaceutical regulatory authority, the General Directorate of Drugs and Pharmacies (Dirección General de Drogas y Farmacias), a unit of the Secretariat of State of Public Health and Social Assistance (SESPAS [ministry of health]). However, the Vaxigrip[®] vaccine packaged in standard, multidose 5 mL vials to be used in this study are not specifically registered in the Dominican Republic, and thus will be imported and administered under special investigational authorization from the national regulatory authority.

10.4.2.1 Product Characteristics

As described in its Canadian product [insert] monograph: AventisPasteur2005

"VAXIGRIP[®] [Inactivated Influenza Vaccine Trivalent Types A and B (Split Virion)] for intramuscular use, is a sterile suspension prepared from influenza viruses propagated in chicken embryos. Following incubation, the virus-containing fluids are collected and clarified and the viruses are concentrated then purified by zonal centrifugation using a sucrose density gradient. Subsequent stages consist of treatment with octoxynol-9 (Triton[®] X-100) to obtain split antigens, then inactivation using formaldehyde solution. The split-antigen is suspended in sodium phosphate-buffered, isotonic sodium chloride solution. The type and amount of viral antigens contained in VAXIGRIP[®] conform to the current requirements of the World Health Organization (WHO)." ^{WHO2005}

The study will commence with the 2006 Southern Hemisphere formulation of Vaxigrip[®] **INF** vaccine, the content of which is summarized in **Table 3**. This formulation becomes available in early 2006 and will expire on 31 December of 2006. It is anticipated that a proportion of vaccinations will occur after that date (see timeline in section 5), requiring use of either or both of the next available formulations (2006-2007 Northern Hemisphere and 2007 Southern Hemisphere). Their content will not be known until after the study begins. If there is a change of strains between formulations used, each participant will receive all his or her doses from the same unexpired formulation.

HIRRC/CDC Needle-free Intradermal	Page 44	File: 4785-ID-INF-Prot-Engl-2008Jun24.doc
Influenza Study - CDC-ISO-4785	of 138	2008-Jun-24

As described in section 9.5.1, the biseasonal epidemiology of influenza in the Dominican Republic justifies use of either Northern or Southern hemisphere formulations. If strains change between seasonal formulations used in the study, serologic assays with appropriate antigens will be segregated accordingly.

Table 3 Vaxigrip [®] INF vaccine content, by study arm	Study Arm	
	"ID-JI-0.1"	"IM-NS-0.25"
2006 Southern Hemisphere formulation	"IM-NS-0.1"	(control)
Hemagglutinin antigen		
A/New Caledonia/20/99 (H1N1) [IVR-116]:	3 µg	7.5 μg
A/New York/55/2004 (H3N2) [NYMC X-157]		
(A/California/7/2004-like):	3 µg	7.5 μg
B/Victoria/2/87 lineage (B/Malaysia/2506/2004-like):	3 µg	7.5 μg
Sodium-phosphate buffered, isotonic sodium chloride solution	up to 0.1 mL	up to 0.25 mL
Formaldehyde	≤6 μg	≤15 μg
Thimerosal preservative	0.4 µg	1 μg
Triton [®] X-100, sucrose, neomycin	Trace	trace

